#### 11.4.2 Non-SAE Reporting

Non-SAEs will be reported to the DF/HCC Overall PI on the toxicity CRFs.

### 11.5 Reporting to the IRBs

Investigative sites within DF/HCC will report all SAEs directly to the DFCI OHRS.

Other investigative sites should report SAEs to their respective IRB according to the local IRB's policies and procedures in reporting AEs. A copy of the submitted institutional SAE form should be forwarded to:

[REDACTED]  
[REDACTED]  
[REDACTED]  
[REDACTED]

The DF/HCC PI will submit SAE reports from outside institutions to the DFCI OHRS according to DFCI IRB policies and procedures in reporting AEs.

CONFIDENTIAL

This document is confidential. Do not disclose or use except as authorized.

## **11.6 Reporting to the FDA**

This study is IND Exempt.

## **11.7 Reporting to Hospital Risk Management**

Participating investigators will report to their local Risk Management office any subject safety reports or sentinel events that require reporting according to institutional policy.

## **11.8 Monitoring of Adverse Events and Period of Observation**

All AEs, both serious and non-serious, and deaths that are encountered from initiation of study intervention, throughout the study, and within 30 days of the last study intervention should be followed to their resolution, or until the participating investigator assesses them as stable, or the participating investigator determines the event to be irreversible, or the participant is lost to follow-up. The presence and resolution of AEs and SAEs (with dates) should be documented on the appropriate case report form and recorded in the participant's medical record to facilitate source data verification.

For some SAEs, the study sponsor or designee may follow-up by telephone, fax, and/or monitoring visit to obtain additional case details deemed necessary to appropriately evaluate the SAE report (e.g., hospital discharge summary, consultant report, or autopsy report).

Participants should be instructed to report any serious post-study event(s) that might reasonably be related to participation in this study. Participating investigators should notify the DF/HCC Overall PI and their respective IRB of any unanticipated death or AE occurring after a participant has discontinued or terminated study participation that may reasonably be related to the study.

## **12. DATA AND SAFETY MONITORING**

### **12.1 Data Reporting**

#### **12.1.1 Method**

The ODQ will collect, manage, and perform quality checks on the data for this study.

#### **12.1.2 Data Submission**

The schedule for completion and submission of case report forms (paper or electronic) to the ODQ is as follows:

CONFIDENTIAL

This document is confidential. Do not disclose or use except as authorized.

Form	Submission Timeline
Eligibility Checklist	Complete prior to registration with ODQ.
On Study Form	Within 14 days of registration.
Baseline Assessment Form	Within 14 days of registration.
Treatment Form	Within 10 days of the last day of the cycle.
AE Report Form	Within 10 days of the last day of the cycle. If AEs are ongoing at the end of the last cycle, continue to submit AE reports until resolution or 30 days post-treatment.
Response Assessment Form	Within 10 days of the completion of the cycle required for response evaluation.
Off Treatment/Off Study Form	Within 14 days of completing treatment or being taken off study for any reason.
Follow up/Survival Form	Within 14 days of the protocol defined follow up visit date or call.

## 12.2 Safety Meetings

The DF/HCC DSMC will review and monitor toxicity and accrual data from this trial. The committee is composed of clinical specialists with experience in oncology and who have no direct relationship with the study. Information that raises any questions about participant safety will be addressed with the Principal Investigator and study team.

The DSMC will review each protocol up to four times a year or more often if required to review toxicity and accrual data. Information to be provided to the committee may include: up-to-date participant accrual; current dose level information; all grade 2 or higher unexpected AEs that have been reported; summary of all deaths occurring within 30 days for Phase I or II protocols; for gene transfer protocols, summary of all deaths while being treated and during active follow-up; any response information; audit results, and a summary provided by the study team. Other information (e.g. scans, laboratory values) will be provided upon request.

## 12.3 Monitoring

Involvement in this study as a participating investigator implies acceptance of potential audits or inspections, including source data verification, by representatives designated by the DF/HCC Overall PI (or Protocol Chair) or DF/HCC. The purpose of these audits or inspections is to examine study-related activities and documents to determine whether these activities were conducted and data were recorded, analyzed, and accurately reported in accordance with the protocol, institutional policy, GCP, and any applicable regulatory requirements.

CONFIDENTIAL

This document is confidential. Do not disclose or use except as authorized.

All data will be monitored for timeliness of submission, completeness, and adherence to protocol requirements. Monitoring will begin at the time of participant registration and will continue during protocol performance and completion.

See section 5.0 of the Data Safety Monitoring Plan (Appendix E) for additional details on monitoring of external sites for this study.

## **13. REGULATORY CONSIDERATIONS**

### **13.1 Protocol Review and Amendments**

This protocol, the proposed informed consent and all forms of participant information related to the study (e.g., advertisements used to recruit participants) and any other necessary documents must be submitted, reviewed and approved by a properly constituted IRB governing each study location.

Any changes made to the protocol must be submitted as amendments and must be approved by the IRB prior to implementation. Any changes in study conduct must be reported to the IRB. The DF/HCC Overall PI (or Protocol Chair) will disseminate protocol amendment information to all participating investigators.

All decisions of the IRB concerning the conduct of the study must be made in writing.

### **13.2 Informed Consent**

All participants must be provided a consent form describing this study and providing sufficient information for participants to make an informed decision about their participation in this study. The formal consent of a participant, using the IRB approved consent form, must be obtained before the participant is involved in any study-related procedure. The consent form must be signed and dated by the participant or the participant's legally authorized representative, and by the person obtaining the consent. The participant must be given a copy of the signed and dated consent document. The original signed copy of the consent document must be retained in the medical record or research file.

### **13.3 Ethics and Research Practices**

This study is to be conducted according to the following considerations, which represent good and sound research practice:

- US CFR governing clinical study conduct and ethical principles that have their origin in the Declaration of Helsinki
  - Title 21 Part 50 – Protection of Human Subjects

CONFIDENTIAL

This document is confidential. Do not disclose or use except as authorized.

- Title 21 Part 54 – Financial Disclosure by Clinical Investigators  
[REDACTED]
- Title 21 Part 56 – Institutional Review Boards  
[REDACTED]
- Title 21 Part 312 – Investigational New Drug Application  
[REDACTED]
- State laws
- DF/HCC research policies and procedures  
[REDACTED]  
[REDACTED]

It is understood that deviations from the protocol should be avoided, except when necessary to eliminate an immediate hazard to a research participant. In such case, the deviation must be reported to the IRB according to the local reporting policy.

#### **13.4 Study Documentation**

The investigator must prepare and maintain adequate and accurate case histories designed to record all observations and other data pertinent to the study for each research participant. This information enables the study to be fully documented and the study data to be subsequently verified.

Original source documents supporting entries in the case report forms include but are not limited to hospital records, clinical charts, laboratory and pharmacy records, recorded data from automated instruments, microfiches, photographic negatives, microfilm or magnetic media, and/or x-rays.

#### **13.5 Records Retention**

All study-related documents must be retained for the maximum period required by applicable federal regulations and guidelines or institutional policies.

#### **13.6 Multi-Center Guidelines**

This protocol will adhere to the policies and requirements of the DF/HCC. The specific responsibilities of the DF/HCC Overall PI (or Protocol Chair), Coordinating Center, and Participating Institutions are presented in the Dana-Farber/Harvard Cancer Center Multi-Center Data and Safety Monitoring Plan (see Appendix E).

CONFIDENTIAL

This document is confidential. Do not disclose or use except as authorized.

- The DF/HCC Overall PI/Coordinating Center is responsible for distributing all IND Action Letters or Safety Reports to all participating institutions for submission to their individual IRBs for action as required.
- Mechanisms will be in place to ensure quality assurance, protocol compliance, and AE reporting at each site.
- Except in very unusual circumstances, each participating institution will order the agent(s) directly from the supplier. A participating site may order the agent(s) only after the initial IRB approval for the site has been forwarded to the Coordinating Center.

CONFIDENTIAL

This document is confidential. Do not disclose or use except as authorized.

## 14. STATISTICAL CONSIDERATIONS

### 14.1 Primary Analysis

The primary objective of this trial is to analyze possible AR related mechanisms of resistance to enzalutamide in serial CRPC biopsies including AR sequencing (mutations, splice variants), AR regulated gene expression, tumor androgen levels, profiling of enzymes involved in androgen synthesis/metabolism, and whole-exome and transcriptome sequencing. These data are of various forms resulting in different measures for a given participant: (a) continuous data will be evaluated by calculating mean percent change in level, (b) ordinal data will be evaluated by the mean percent change in count, and (c) categorical binary data will be evaluated by No/Yes change in status.

For the primary analysis, only participants who received at least 2 cycles of enzalutamide and experienced progression will be eligible. We plan to enroll a total of 66 participants to obtain 40 evaluable participants. A 60% overall yield is based on the assumptions that 95% of participants are eligible, 90% of these participants have paired biopsies and 70% of participants have evaluable tumors for each sample.

The target sample size is based on power to evaluate a mean percent change in level. The hypothesis is that AR reactivation can lead to resistance to enzalutamide. We will evaluate the mean percent change in a set of resistance parameters using the paired t-test. All continuous variables will be evaluated as a set. A mean percent change of 30% would be considered biologically significant. The effect size is defined as the mean percent change divided by the standard deviation (SD) of percent change, which is unknown in this population. The table below provides the mean percent change that can be detected with 80% or 90% power under various scenarios of SD given a one-sided 0.025 alpha and 40 evaluable participants. For example, there is 80% power to detect mean percent change of 22.7% given a SD of 50% corresponding to an effect size=0.454 SD. The mean percent change presented ranges from 13.6%-31.5%. Therefore, this study is designed with satisfactory power to show a biologically significant mean percent change in a set of resistance parameters.

Paired Tumor Samples (n=40)				
	Paired t-test, 1-sided alpha=0.025			
Power=80%, Effect Size=0.454 SD				
Standard Deviation	30%	40%	50%	60%
Mean Percent Change	13.6%	18.2%	22.7%	27.3%
Power=90%, Effect Size=0.526 SD				
Standard Deviation	30%	40%	50%	60%
Mean Percent Change	15.8%	21.0%	26.3%	31.5%

CONFIDENTIAL

This document is confidential. Do not disclose or use except as authorized.

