### 8.1 Statistical Data Analysis

Determination of biological and molecular endpoints to analyze possible AR related mechanisms of resistance to enzalutamide in serial tumor biopsies will occur as follows:

- AR sequencing
  - Mutations – continuous variable from microarray data
  - TMPRSS2:ERG translocation status – categorical variable from PT PCR (yes vs. no)
  - AR splice variants – categorical variable from RT PCR (native vs. alternative)
- AR regulated gene expression – continuous variable from microarray data
- Tumor androgen levels – continuous variable from mass spectroscopy data
- Profiling of enzymes involved in androgen synthesis/metabolism – continuous variable from microarray data

CONFIDENTIAL

This document is confidential. Do not disclose or use except as authorized.

- Whole-exome and transcriptome sequencing – continuous variable from sequencing analysis

Continuous data will be evaluated by calculating mean percent change in level. Categorical data will be evaluated by yes/no change in status. Ordinal/count number data will be evaluated by mean percent change in total count.

CONFIDENTIAL

This document is confidential. Do not disclose or use except as authorized.

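### Paired binary markers are summarised only as changed or not, so the reported rate cannot separate gain of an AR splice variant from loss

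*Combined protocol and SAP*

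**What the plan says.** Section 14.1 (Primary Analysis) sorts the biopsy data by type. Continuous and ordinal data are measured by mean percent change. For binary data, "categorical binary data will be evaluated by No/Yes change in status". Section 8.1 (Statistical Data Analysis) gives the same rule with the two words reversed: "Categorical data will be evaluated by yes/no change in status".

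Section 8.1 lists two binary markers: AR splice variants (native or alternative) and TMPRSS2:ERG translocation status (yes or no). Splice variants are named in the primary objective (sections 1.2 and 14.1). TMPRSS2:ERG is not. It appears in a secondary objective on correlation with response (section 1.3) and in the section 8.1 list.

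The stated hypothesis has a direction: "The hypothesis is that AR reactivation can lead to resistance to enzalutamide". The primary test covers continuous measures only: "We will evaluate the mean percent change in a set of resistance parameters using the paired t-test". It is sized "given a one-sided 0.025 alpha and 40 evaluable participants". The one test named for categorical markers is Fisher's exact test against response, in section 14.2. That is not a before-and-after comparison.

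**The concern.** A marker measured at baseline and at progression has four possible outcomes: stable negative, stable positive, gained, lost. A yes/no change score merges the last two. For splice variants they carry opposite messages. Section 2.4 describes variants lacking the ligand-binding domain as a route to constitutive AR signalling and to enzalutamide resistance. A move from native to alternative therefore fits the hypothesis, and a move back does not. The paired t-test keeps the sign of change for continuous measures. The binary rule drops it.

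The pooled rate also has no natural null value of zero. Any assay or sampling error makes it positive when nothing has changed. Some error is plausible: section 3.1.5 lets the radiologist choose the site for tissue yield and safety, and neither section 5 nor the Study Calendar notes require the progression biopsy to come from the same lesion.

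At stake is whether the splice-variant result can be read as evidence for or against the hypothesis.

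**Working it through.** **1. The plan's own figures.** Inputs from section 14.1: n = 40 pairs, one-sided alpha 0.025, effect sizes 0.454 and 0.526 SD. Noncentral-t power with 39 degrees of freedom and noncentrality (effect size) × √40 gives 79.96% and 90.04%, matching the stated 80% and 90%. The yield is 66 × 0.95 × 0.90 × 0.70 = 39.5, about 40. These figures reproduce, and all the power figures concern continuous change. The plan states no figure for the binary markers.

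**2. What one reported rate can hide.** No error rate is needed here. Take 8 of 40 changed: 20%, exact 95% CI 9.1% to 35.6%. Among g gains and l losses, the exact McNemar one-sided p is P(X ≥ g), with X binomial (g + l, 0.5).

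| Gains / losses | Reported | One-sided p | Two-sided p |
|---|---|---|---|
| 8 / 0 | 20% | 0.5^8 = 0.004 | 0.008 |
| 6 / 2 | 20% | 37/256 = 0.14 | 0.29 |
| 4 / 4 | 20% | 163/256 = 0.64 | 1 |
| 0 / 8 | 20% | 1.0 | 0.008 (opposite direction) |

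**3. What error alone would produce.** The documents give no misclassification rate, so e per biopsy is an assumption, independent and equal at both times. With no true change, P(scored as changed) = 2e(1 − e).

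| e (assumed) | 2e(1 − e) | Expected changed in 40 | False-positive rate, exact McNemar, one-sided 0.025 |
|---|---|---|---|
| 1% | 0.0198 | 0.8 | below 0.1% |
| 5% | 0.095 | 3.8 | 0.2% |
| 10% | 0.18 | 7.2 | 0.8% |

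The errors need not be symmetric. With prevalence p, sensitivity se and specificity sp the same at both times, P(gain) = p(1 − se)se + (1 − p)(1 − sp)sp, and P(loss) is the same expression. For example, with se = 85%, sp = 97% and p = 30% (all assumed), each is 5.9%, or 4.7 pooled changes in 40. Error adds up in the pooled count but balances in expectation between gain and loss.

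**4. Power of the directional comparison.** Sum over the number of discordant pairs D, binomial (40, P(gain) + P(loss)), the probability that gains reach the exact one-sided 0.025 limit for that D. With a loss rate of 4.75% (half of 9.5%, the e = 5% case), power is about 38% for 20% gain and about 76% for 30% gain.

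**The case against.** The best defence is that section 14.1 defines a score for each participant, not a rule for reporting across participants. Nothing says that gains and losses must be added together, and both statuses must be recorded to score a change, so the 2x2 table can always be recovered. The section 14.1 wording could even be read as a move from no to yes. Part of this stands: pooling is the natural reading, not an explicit instruction, and no data are lost. But the reversed order in section 8.1 tells against the no-to-yes reading, and neither section commits the analyst to showing direction.

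A reader might infer more than the documents support:

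- **That random switching would be declared acquired resistance, or that type I error is inflated.** The plan has no threshold, null rate or test that turns a change in a binary marker into a finding, and it does not rank markers.
- **That TMPRSS2:ERG weakens the primary objective in the same way.** It is not named there, and the documents give it no resistance direction. Its stated use is correlation with response, which section 14.2 calls exploratory.
- **That noise alone would give very high change rates.** Under the formula above, 40% changed needs e of about 28%, well outside the 1% to 10% range used here.

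**Conclusion.** The point holds in a limited form. Sections 14.1 and 8.1 summarise paired binary markers without direction while the hypothesis has one. As written, the splice-variant result in the primary objective could not be interpreted: one reported rate is compatible with a clear shift towards resistance, no shift, or a shift away from it. That conclusion needs no assumption beyond the natural reading of the rule.

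The noise estimate of 0.8 to 7.2 of 40 pairs rests on an assumed error rate of 1% to 10%, independent and equal in both biopsies. It shows the scale and is not a prediction. The target of 66 enrolled and 40 evaluable, the power table and the paired t-test are untouched. The wording should be changed, but the primary continuous analysis does not depend on it.

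**What to change.** In sections 14.1 and 8.1:

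- State for each binary marker which direction counts as resistance, where one exists. For splice variants this is native to alternative. For TMPRSS2:ERG, say that no direction is specified.
- Replace the yes/no change with the paired baseline-by-progression 2x2 table, and report percent gained and percent lost with exact confidence intervals. Percent gained should not stand alone, because under the error model above it still contains half of the random switches.
- Compare gain with loss by an exact McNemar test: one-sided 0.025 where a direction is stated, to match the plan, and two-sided otherwise. Label it supportive or exploratory.

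The cost is wording and one small extra analysis on the same data, with no added participants, biopsies or assays. The drawback is the modest power at 40 pairs shown above, so a non-significant comparison should not be read as evidence of no shift.

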**Number of Subjects/Study Duration:**

We plan to enroll a total of 66 participants to obtain 40 evaluable participants. Assuming an accrual rate of 6 participants per month, enrollment will take 11 months. Participants will be treated with enzalutamide 160 mg orally per day. We will assess PSA at baseline and day 1 of each 28-day cycle until radiographic progression defined by PCWG2. Participants will continue on therapy until radiographic or symptomatic progression or taken off study for another reason.

**14.2 Analysis of Secondary Endpoints**

Safety and tolerability of enzalutamide will be evaluated. All participants who receive at least 1 dose of study drug will be included in these analyses. A summary of all Grade 1-4 treatment-related toxicities will be provided by toxicity type and maximum grade. The maximum grade consolidates the reports of a given type of toxicity for a participant over time by taking the maximum grade across time (i.e. a participant appears only once for a given type of toxicity). Participants with reports of multiple toxicities of different types are reported multiple times under the relevant toxicity categories. ‘Treatment-related’ toxicities are defined by an attribution as possible, probable or definite. With 66 participants, the maximum width of a 90% CI for a given toxicity rate is 22%. The probability of observing at least one rare severe toxicity (true rate=5%) is 95%. The number of cycles completed with and without dose modifications and treatment delays.

PSA response to enzalutamide will be summarized as frequency and percent. Participants who are unevaluable for response will be included in the denominator as nonresponders when calculating the response rate. Duration of PSA response for the regimen of enzalutamide will be defined relative to the first achievement of PSA response and will be estimated using the method of Kaplan and Meier. PSA response will be measured according to PCWG2 (2008) criteria.

Participants with measurable disease will be evaluated for response using RECIST 1.1 criteria. Duration of response of bone lesions or measurable disease will be described using Kaplan-Meier estimates.

The set of AR resistance measures will be summarized using descriptive statistics (mean, median, standard deviation (SD), interquartile range (IQR)). Correlation among measures will be assessed graphically with scatter plots and using Pearson correlation coefficients (or Spearman if appropriate).

The two-group t-test will be used to examine the difference in level and/or change pre- to post-treatment in levels by PSA and RECIST (measurable disease participants) response outcome. Assuming 40 evaluable participants, if PSA response rate is 25% (10 responders and 30 non-responders), there is 80% power to detect an effect of 1.05 SD at a two-sided significance level of 0.05. Continuous levels may be dichotomized at the median for further evaluation. Association between response and categorical variables will be evaluated using Fisher’s exact test. Analyses of these correlative endpoints will be exploratory and adjustments will not be made for multiple comparisons.

CONFIDENTIAL

This document is confidential. Do not disclose or use except as authorized.

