#### *Falls and Fall-related Injuries*

In the randomized clinical trial, falls or injuries related to falls occurred in 4.6% of patients treated with enzalutamide compared to 1.3% of patients on placebo. Falls were not associated with loss of consciousness or seizure. Fall-related injuries were more severe in patients treated with enzalutamide and included non-pathologic fractures, joint injuries, and hematomas.

CONFIDENTIAL

This document is confidential. Do not disclose or use except as authorized.

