- l: For DFCI participants only, one bed position of quantitative SPECT/CT will be performed as an imaging substudy concurrently with the standard of care bone scans at baseline and at the time of the first two follow up standard of care bone scans. The field of view will be determined by the nuclear medicine physician depending on the location of the lesions on the planar images.
- m: Study agent is enzalutamide. Subjects will be continued on LHRH agonist/antagonist as prescribed. Subjects will begin taking study agent on Day 1/Cycle 1.
- n: AEs should be collected from the date informed consent is signed until 30 days after discontinuation from the study.
- o: Tumor biopsy must be performed prior to starting study medication. Participants will need to be screening and registered before having a biopsy. Friday should be avoided due to difficult of processing bone biopsies on the weekend. For DFCI participants, if the biopsy site (baseline and progression) is a pelvic bone both an aspirate and core biopsy will be obtained.
- p: Participants who stop the protocol therapy before receiving four cycles of enzalutamide will not be asked to undergo the second biopsy. The tumor biopsy at the end of the study can be done +/- 14 days of the determination of progression. Enzalutamide will be discontinued following completion of the second biopsy. Situations where the participant stops protocol therapy for reasons other than progression after receiving four cycles of enzalutamide should be discussed with the PI if it felt that the biopsy would not represent progressive disease.
- q: The End of Treatment Visit will be the visit at which it is determined that the patient will no longer be taking treatment given disease progression, toxicity, or other reason.
- r: Follow up Visits: Participants will be followed for up to 5 years post-study discontinuation or until death, whichever comes first. Participant follow up visits will be at the research clinic for the first 2 years of follow-up. Following the first 2 years, participant follow-up can be done via medical record review and/or by phone. Participants will be followed for subsequent lines of therapy, including line of agent, name of agent, and PSA kinetics following study drug discontinuation and correlate with response to study drug. This information will be updated every 6 months. The research team will collect this information during patient clinic visits, by phone, or via medical record review.

CONFIDENTIAL

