## 11. ADVERSE EVENT REPORTING REQUIREMENTS

### 11.1 Definitions

#### 11.1.1 Adverse Event (AE)

An AE is any undesirable sign, symptom or medical condition or experience that develops or worsens in severity after starting the first dose of study treatment or any procedure specified in the protocol, even if the event is not considered to be related to the study.

Abnormal laboratory values or diagnostic test results constitute AEs only if they induce clinical signs or symptoms or require treatment or further diagnostic tests.

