### 11.1.4 Attribution

Attribution is the relationship between an AE or SAE and the study treatment. Attribution will be assigned as follows:

- Definite – The AE is clearly related to the study treatment.
- Probable – The AE is likely related to the study treatment.
- Possible – The AE may be related to the study treatment.
- Unlikely - The AE is doubtfully related to the study treatment.
- Unrelated - The AE is clearly NOT related to the study treatment.

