## 11.2 Procedures for AE and SAE Recording and Reporting

CONFIDENTIAL

This document is confidential. Do not disclose or use except as authorized.

Participating investigators will assess the occurrence of AEs and SAEs at all participant evaluation time points during the study.

All AEs and SAEs whether reported by the participant, discovered during questioning, directly observed, or detected by physical examination, laboratory test or other means, will be recorded in the participant's medical record and on the appropriate study-specific case report forms.

The descriptions and grading scales found in the revised NCI CTCAE version 4.0 will be utilized for AE reporting. All appropriate treatment areas should have access to a copy of the CTCAE version 4.0.

A copy of the CTCAE version 4.0 can be downloaded from the CTEP website at: [http://ctep.cancer.gov/protocolDevelopment/electronic\\_applications/ctc.htm](http://ctep.cancer.gov/protocolDevelopment/electronic_applications/ctc.htm).

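### The only prespecified toxicity table covers Grade 1-4 treatment-related events, so biopsy-only complications, events rated unlikely or unrelated, and all Grade 5 events have no planned summary

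*Combined protocol and SAP*

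**What the plan says.** Assessing the safety and tolerability of enzalutamide is a secondary objective (Section 1.3). Section 14.2 includes everyone who received at least one dose and specifies the output: "A summary of all Grade 1-4 treatment-related toxicities will be provided by toxicity type and maximum grade". It then narrows the scope, since treatment-related "toxicities are defined by an attribution as possible, probable or definite". Apart from a line on cycles, dose modifications and delays, Section 14 plans no other safety summary. There is no all-cause AE table, no SAE table, no Grade 5 summary and no summary of biopsy complications.

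Collection is much wider than the table. Section 11.1.1 defines an AE as one that develops or worsens "after starting the first dose of study treatment or any procedure specified in the protocol, even if the event is not considered to be related". Section 11.2 sends to the medical record and the case report forms "All AEs and SAEs whether reported by the participant, discovered during questioning, directly observed, or detected by physical examination", or by laboratory test or other means.

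Attribution has a single target. Section 11.1.4 states: "Attribution is the relationship between an AE or SAE and the study treatment". Section 7.1.10 equates study treatment with enzalutamide, and Section 7.1.6 says that no other treatment agent is given. None of the five attribution categories refers to a study procedure.

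**The concern.** The data are collected without regard to cause, and the only planned table then filters them by cause and by grade. The filter matters for three reasons.

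- **Biopsies.** Tissue from a baseline and a progression biopsy is the basis of the primary objective. A complication caused only by the needle cannot properly be called possibly related to enzalutamide, so it is excluded by definition.
- **Single-arm attribution.** There is no control arm, and the investigator knows that every participant is on the drug. In the randomized trial described in Section 6.1.1, grade 3 or higher reactions were reported in 47% of patients on enzalutamide and 53% on placebo. Background events are thus common, and the rating of an individual event rests largely on judgement. The protocol's own signal for falls came from comparing arms: "falls or injuries related to falls occurred in 4.6% of patients treated with enzalutamide compared to 1.3% of patients on placebo".
- **Deaths.** The Grade 1-4 limit removes fatal events even when they are attributed to the drug.

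At stake is whether the reported safety result describes what happened to the participants, or only what investigators ascribed to the drug short of death.

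**Working it through.** **Inputs.** From Section 14.2: n = 66, a true toxicity rate of 5%, a stated 95% chance of at least one event, and a stated maximum 90% CI width of 22%. From Section 6.1.1: falls 4.6%. From Section 14.1: 95% eligible, and 90% of these with paired biopsies. One input is an assumption: f, the share of events rated at least possible. The documents give no value for it, so a range is shown.

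**1. The plan's own figures.** P(at least one) = 1 − 0.95^66 = 0.966, against the stated 95%. The maximum Wald width is 2 × 1.645 × 0.5/√66 = 20.2%. Adding 1/66 for continuity gives 21.8%, and the exact interval gives 21.4%, against the stated 22%. Both figures reproduce.

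**2. What the filter does to them.** If a toxicity has true rate p and a share f is rated related, it enters the planned table at rate p × f. The expected count is 66 × p × f, and the chance of at least one is 1 − (1 − p × f)^66.

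| f (assumed) | 5% toxicity: expected | P(at least one) | Falls at 4.6%: expected | P(at least one) |
|---|---|---|---|---|
| 1 (all-cause table) | 3.30 | 96.6% | 3.04 | 95.5% |
| 0.75 | 2.48 | 92.0% | 2.28 | 90.1% |
| 0.50 | 1.65 | 81.2% | 1.52 | 78.5% |
| 0.25 | 0.83 | 56.4% | 0.76 | 53.4% |

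The plan's 95% therefore carries over to the planned table only if nearly every such event is rated at least possible.

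**3. What falls outside, and why.**

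- *Complication due only to a biopsy:* recorded as an AE under 11.1.1, but 11.1.4 has no matching attribution target. It is excluded by definition.
- *Event rated unlikely or unrelated to enzalutamide:* recorded under 11.2, excluded by the attribution rule in 14.2.
- *Grade 5 event:* excluded by the grade limit, whatever the attribution. The infection or sepsis deaths in Section 6.1.1 (1.0% versus 0.3%) belong here.

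**4. Number of biopsies.** There are up to 66 baseline biopsies among planned participants. On the plan's yield assumptions there are 66 × 0.95 × 0.90 = 56.4, so about 56, second biopsies.

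**5. Whether baseline-biopsy events are captured at all.** The Study Calendar (Section 9, footnote o) places the baseline biopsy before the first dose. Footnote n says "AEs should be collected from the date informed consent is signed until 30 days after discontinuation from the study". Section 6, however, starts AE collection at the first dose, and Section 11.4.1 starts SAE reporting after the initial dose. Under the calendar, baseline-biopsy events are captured; under Section 6 they are not. The at-least-one-dose population would also leave out anyone biopsied but never treated.

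**The case against.** The strongest reply has four parts.

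- **Falls and infections may well enter the table.** Both are described under Anticipated Toxicities in Section 6.1, and a rating of possible is enough. This stands. A reader might infer that such harms are usually judged unrelated, but nothing in the documents says so.
- **Infections are a poor example of attribution loss.** This also stands. The excess reported is in deaths, which the grade limit removes. Infection-related SAEs were about 6% in both arms, so no excess is shown there.
- **The objective concerns enzalutamide, not biopsies, and background events are not drug toxicity.** This stands in part. With 53% on placebo against 47% on enzalutamide, leaving out background events does not by itself bias an estimate of drug toxicity downwards, and an uncontrolled all-cause table cannot isolate the drug effect either. But an all-cause count does not depend on unblinded attribution. The protocol's own AE definition also brings procedure events into scope. The second biopsy is not universal: those stopping before four cycles are not asked for it (Section 5).
- **Events are visible elsewhere.** The DSMC may receive unexpected grade 2 or higher AEs and deaths within 30 days (Section 12.2), and SAEs are reported individually (Section 11.4.1). These are oversight channels, not results. Section 14.2 does not forbid further tables, so it would be wrong to say that these events can never be reported. They are simply not prespecified.

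**Conclusion.** The point holds as a gap between what is collected and what is planned for reporting. Followed as written, Section 14.2 omits biopsy-only complications, events rated unlikely or unrelated, and all Grade 5 events.

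The size of the omission cannot be derived from the documents. The fall from 96.6% to 81% or 56% for a 5% toxicity rests on assumed related shares of one half and one quarter, and shows sensitivity only. A reader might apply the 47% grade 3 or higher rate to 66 participants (66 × 0.47 ≈ 31) and state how many would vanish from the table. The documents do not support that, because any share called unrelated would be a guess. The 47% also comes from a docetaxel-pretreated population, whereas Section 3.1.8 allows prior cytotoxic regimens without requiring any.

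The primary analysis and the sample size are unaffected.

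**What to change.** - **Section 14.2:** make the main safety output tables of all AEs and all SAEs regardless of attribution, by type and maximum grade, including Grade 5. Keep the treatment-related table as a subset.
- **Section 11.1.4 and the AE form:** record relation to the protocol biopsy separately from relation to enzalutamide.
- **Biopsy complications:** list them with the number of biopsies performed as the denominator, by baseline and progression, and include participants biopsied but never dosed.
- **AE collection start:** reconcile Section 6 (first dose) with the Study Calendar (consent), and check Section 11.4.1 against the result. Without this, the baseline half of the biopsy listing may have no data behind it.

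The cost is a few extra tables and one form field. On-treatment AEs are already collected. Baseline-biopsy events may need a clarified collection rule. No change to sample size is needed.
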